# Evaluation of low-cost techniques for detecting sickle cell disease and $\beta$ -thalassemia in Nepal

# 1.0 Background

## 1.1 Sickle cell disease

Sickle cell disease (SCD) is a collection of inherited blood disorders, and is a multisystem disorder affecting nearly every organ in the body [1]. The disease primarily causes erythrocytes or red blood cells (RBCs) to be distorted and rigid due to polymerization (e.g. during deoxygenation), often changing them to crescent or sickle shaped cells [2]. Other cascading effects include hemolytic anemia, blockage of microvasculature (capillaries and small blood vessels), episodes of acute illness (such as vaso-occlusive pain crisis or sickle cell crisis), and progressive organ damage [3], [4]. The chances of survival and quality of life drastically increase with early diagnosis, newborn screening, penicillin prophylaxis, pneumococcal immunization, blood transfusion, hydroxyurea treatment, hematopoietic stem-cell transplantation, and education about disease severity and complications [1], [4].

SCD is one of the most common monogenic diseases worldwide and results from mutations in the  $\beta$ -globin gene [1], [3]. The most common and severe form of SCD is sickle cell anemia (SCA), caused by the inheritance of  $\beta^S$  alleles or the variant HbS (hemoglobin S or sickle hemoglobin) genes from both parents – resulting in the homozygous form HbSS, instead of the normal homozygous form HbAA. Another form of SCA is HbS/ $\beta^0$  thalassemia, caused by the inheritance of a  $\beta^0$  thalassemia mutation from one parent and an HbS gene from another, resulting in no normal HbA and a majority of HbS. The heterozygous form HbAS, known as sickle cell trait (SCT), affects millions of people worldwide and is usually not associated with hematological abnormalities [2]. On the other hand, compound heterozygous conditions are associated with mild to severe clinical courses and are also categorized as SCD. Some compound heterozygous conditions include HbS with hemoglobin C or HbC (HbSC), HbS with  $\beta$ -thalassemia (HbS/ $\beta^0$ -thalassemia or HbS/ $\beta^+$ -thalassemia), and HbS with other  $\beta$  globin variants (e.g. HbSD and HbSOArab) [1], [3], [4].

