#### 1.3 Global burden of disease

Over the next 30 years, it is estimated that 15 million babies will be born with SCD globally, and 50-90% of infants born with SCD in low-income countries will die before 5 years of age [6]. The burden of the disease is much greater in lower-resource settings [4], with around 90% of SCD occurring in low- and middle-income countries [7]. The highest prevalence has been found in sub-Saharan Africa, where approximately 230,000 children are born with SCD every year (0.74% of births in the region). In contrast, 2600 and 1300 children are born with SCD in North America and Europe, respectively [3]. In addition to screening for SCD, it is also essential to screen for SCT (heterozygous HbAS) because parents with SCT can give birth to children with SCD (homozygous HbSS or compound heterozygous forms). The number of babies born with SCT worldwide is estimated to be approximately 5.5 million, and the prevalence is estimated to be 2-30% in African countries [4]. Additionally, around 130,000 children are born with severe hemoglobinopathies such as HbSC and thalassemia annually [8].

In countries with newborn screening and treatment options, like the US and UK, the survival of children with SCA is similar to that of healthy children and adults can live up to their sixties [5]. However, in low-resource settings without newborn screening and treatments such as penicillin prophylaxis and pneumococcal immunization, the mortality rate for children with SCD is tremendously high [4]. In addition, the mortality rates are inaccurate due to lack of adequate screening, and improper diagnosis and management – SCD can be a predisposing factor for

deaths resulting from pneumonia, malaria, tuberculosis, HIV, and diarrheal disease [4], [8]. SCD does not just adversely affect the people involved, but also their families, with increased financial and psychosocial burden [8].

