In areas where HbS is prevalent with other hemoglobin variants (such as  $\beta$ -thalassemia, HbC, etc.), it is essential to identify all the hemoglobin variants possible. If screening techniques that only detect HbS are used in such areas, then compound heterozygous cases (such as HbS/ $\beta$ -thalassemia) could be wrongly diagnosed. Additionally, asymptomatic heterozygous cases (such as HbA/ $\beta$ -thalassemia) may be missed in the screening tests for HbS, and parents with such heterozygous cases can still possibly pass on the variant gene to their children to result in compound heterozygous forms of SCD. Recent studies have indicated a high prevalence of  $\beta$ -thalassemia in Nepal, with approximately 26% - 70% of hemoglobinopathies involving  $\beta$ -thalassemia [11], [12]. Therefore, screening techniques in Nepal should ideally include detection of  $\beta$ -thalassemia in addition to SCD/SCT.

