# 3.0 Hypothesis

We hypothesize that

1. Gazelle diagnostic device can detect  $\beta$ -thalassemia and SCD/SCT with an overall accuracy greater than 90%, compared with HPLC as the reference test

- 2. an automated sickling test (standard sickling test enhanced using low-cost microscopy and machine learning) has a higher overall accuracy than conventional screening techniques (solubility and sickling tests) to detect hemoglobin S in blood samples
- 3. the automated sickling test can additionally classify SCD, SCT and healthy individuals with a sensitivity greater than 90%, based on morphology changes of red blood cells, unlike conventional sickling or solubility tests that do not distinguish between SCD and SCT cases

Overall, we hypothesize that an assessment of the performance and accuracies of low-cost point-of-care techniques (automated sickling test, solubility test, lateral-flow assays, Gazelle Hb variant test) against HPLC tests will provide researchers and health workers with feasible alternative options for screening and detecting SCD, SCT and  $\beta$ -thalassemia in a variety of situations based on the needs of the communities and the resources available.

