## 6.3 Statistical Analysis Plan

Considering HPLC as the reference test, the sensitivity, specificity, positive predictive value (PPV) and negative predictive value (NPV) of the index tests or low-cost techniques (automated

sickling test, HbS solubility test, HemoTypeSC, Sickle SCAN, and Gazelle Hb variant test) will be evaluated.

For each case, the following definitions apply:

- True positive (TP): indicates a positive result for both the index test and the reference test
- True negative (TN): indicates a negative result for both the index test and the reference test
- False positive (FP): indicates a positive result for the index test, but a negative result for the reference test
- False negative (FN): indicates a negative result for the index test, but a positive result for the reference test

The following metrics will be calculated using the total number of TP, TN, FP, and FN:

Sensitivity = 
$$\frac{TP}{TP + FN} \times 100\%$$
  
Specificity =  $\frac{TN}{FP + TN} \times 100\%$   
 $PPV = \frac{TP}{TP + FP} \times 100\%$   
 $NPV = \frac{TN}{TN + FN} \times 100\%$ 

The metrics (sensitivity, specificity, PPV, and NPV) for the index tests will be calculated for the following two categories:

- 1. **Detection analysis by hemoglobin variant** (HbA, HbS, HbC, β-thalassemia): Heterozygous or homozygous forms containing a particular hemoglobin variant in both the index test and the reference test are true positive results for that variant. Test results lacking a particular hemoglobin variant in both index and reference tests, irrespective of other variants present, are true negative results for that variant. The following hemoglobin variants will be analyzed for the index tests.
  - HbS Solubility: HbA, HbS
  - Automated sickling: HbA, HbS
  - HemoTypeSC: HbA, HbS, HbC
  - Sickle SCAN: HbA. HbS. HbC
  - Gazelle Hb Variant: HbA, HbS, HbC, β-thalassemia
- 2. **Detection analysis by phenotype**: In this analysis, the metrics for homozygous and heterozygous states will be calculated differently. The following phenotypes will be analyzed for the index tests.
  - Automated sickling: HbAA, HbAS, HbSS, Overall
  - HemoTypeSC: HbAA, HbAS, HbSS, (HbAC, HbSC, HbCC), Overall
  - Sickle SCAN: HbAA, HbAS, HbSS, (HbAC, HbSC, HbCC), Overall
  - Gazelle Hb Variant: HbAA, HbAS, HbSS, HbS/β-thalassemia, HbA/β-thalassemia, Hbβ/β-thalassemia, (HbAC, HbSC, HbCC), Overall

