## 13. Limitations

Many SCD and  $\beta$ -thalassemia patients will be undergoing treatment and taking medications, which could potentially affect the interpretability of results of the sickling test. Nevertheless, blood films of patients with treatment are expected to include sickled cells during the sickling test. The analyses (e.g. machine learning training) will include information of whether or not patients have had treatment or medication, and any differences in results due to the treatment will be reported.

The population of patients in Nepalgunj are mostly of South Asian descent with possibly different haplotype than that of patients elsewhere (e.g. in Africa). This may have some

implications in differentiating SCD vs. SCT elsewhere, if the machine learning algorithm is only trained using a population of different haplotypes. To improve the accuracy of the machine learning classification, it may be required to add data from the population being tested.

In addition to the homozygous HbSS form of SCA, other heterozygous forms of  $\beta$ -thalassemia (with HbS) could lead to similar levels of sickling. It is unclear whether these can be differentiated in the sickling test. Additionally, the lateral flow assays (HemoTypeSC and Sickle SCAN) do not detect  $\beta$ -thalassemia.

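### For the automated sickling test, the 20 HbS/β-thalassemia participants have no reference class, so they never enter the SCD sensitivity that Hypothesis 3 relies on

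*Combined protocol and SAP*

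**What the plan says.** **The claim.** Section 3.0, Hypothesis 3, states that "the automated sickling test can additionally classify SCD, SCT and healthy individuals with a sensitivity greater than 90" percent. The second objective in 4.0 poses the same three-way question.

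**What counts as SCD.** The documents give two answers.
- Section 1.1 says "compound heterozygous conditions are associated with mild to severe clinical courses and are also categorized as SCD" and names HbS with β-thalassemia among these conditions. Section 1.3 repeats the broad reading: "parents with SCT can give birth to children with SCD (homozygous HbSS or compound heterozygous forms").
- Section 6.3 (sample size paragraph) and 7.2.1 label the SCD group as HbSS, and list 20 people with HbS/β-thalassemia as a group of their own.

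**How the test is scored.** The phenotype analysis in 6.3 reads "Automated sickling: HbAA, HbAS, HbSS, Overall". The Gazelle line in the same list does have the extra rows: "Gazelle Hb Variant: HbAA, HbAS, HbSS, HbS/β-thalassemia, HbA/β-thalassemia, Hbβ/β-thalassemia, (HbAC, HbSC, HbCC), Overall". A false negative is a case that "indicates a negative result for the index test, but a positive result for the reference test". *Overall* is not defined, and no section ties Hypothesis 3 to particular rows.

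**What is acknowledged.** Section 13 notes that forms combining HbS with β-thalassemia may sickle much as HbSS does, and adds: "It is unclear whether these can be differentiated in the sickling test". No scoring rule follows.

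**The concern.** The hypothesis is about a disease class, whereas the analysis rows are genotypes, and one enrolled genotype that the background counts as SCD falls between them. For the automated test, HbS/β-thalassemia is reference-negative in every named row. The error that matters for a three-way classifier, SCD called something else, therefore cannot be recorded as an SCD miss for half of the 40 enrolled people who meet the broad definition. A correct SCD call for the same people is marked as an error in the HbSS row.

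This bears on the reason for running the study in Nepal. Section 1.4 warns: "If screening techniques that only detect HbS are used in such areas, then compound heterozygous cases" may receive the wrong diagnosis. The long-term objectives in 4.0 include using the trained SCD/SCT/healthy classifier for screening there. A result above 90% that rests on HbSS alone would not show how the classifier handles compound heterozygotes.

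**Working it through.** **Inputs**
- Six groups of about 20 (6.3, 7.2.1). 6 × 20 = 120 reproduces the stated total. The plan gives no power or precision target to check.
- From 6.3: sensitivity = TP/(TP + FN); specificity = TN/(FP + TN); PPV = TP/(TP + FP).
- Target: sensitivity above 90% (Hypothesis 3).
- *k* = number of the 20 HbS/β-thalassemia participants not called SCD. The documents give no estimate, so *k* is an assumption and its full range is 0 to 20.

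**Step 1. The rows as written.** The HbSS row has 20 reference positives. It exceeds 90% at 19/20 = 95.0% (exact 95% interval 75.1 to 99.9) or 20/20 = 100% (83.2 to 100). *k* does not enter the formula, so the figure is the same for every *k*.

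**Step 2. Where the 20 go instead.** Keep all 120, assume HbSS and HbAS are all called correctly, and assume no HbS-free participant is called HbAS or HbSS.
- All 20 called HbAS: HbAS sensitivity stays 20/20, HbAS specificity is (100 − 20)/100 = 80%, and HbAS PPV is 20/(20 + 20) = 50%. HbSS sensitivity is unchanged.
- All 20 called HbSS: HbSS specificity is 80/100 = 80% and PPV is 20/40 = 50%, although these calls are right under 1.1.
- Any called HbAA: they lower HbAA specificity and PPV and are HbS false negatives in the variant analysis. HbSS sensitivity is again unchanged.

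**Step 3. SCD as HbSS plus HbS/β-thalassemia.** With *h* HbSS participants called SCD, sensitivity = (*h* + 20 − *k*)/40. Exceeding 90% needs at least 37/40.

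| *k* (assumed) | *h* = 20 | *h* = 19 |
|---|---|---|
| 0 | 40/40 = 100% | 39/40 = 97.5% |
| 2 | 38/40 = 95.0% | 37/40 = 92.5% |
| 3 | 37/40 = 92.5% | 36/40 = 90.0% |
| 4 | 36/40 = 90.0% | 35/40 = 87.5% |
| 10 | 30/40 = 75.0% | 29/40 = 72.5% |
| 20 | 20/40 = 50.0% | 19/40 = 47.5% |

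The target is missed from *k* = 4 if HbSS is perfect, and from *k* = 3 if one HbSS case is also missed. The exact 95% interval for 36/40 is 76.3 to 97.2.

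**Step 4. Whether *Overall* rescues it.** Pooled over the three named rows, it covers 60 people and leaves these 20 out. As three-class agreement over all 120 with no other errors, it is (120 − *k*)/120: 96.7% at *k* = 4, 90.0% at *k* = 12, 83.3% at *k* = 20. Even the reading that includes them dilutes the error.

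**Step 5. Denominators.** Section 7.8 holds out about 10% of images for testing. Split by participant, that is about 0.10 × 120 = 12 people, or 2 per group. The denominators of 20 and 40 are therefore upper limits.

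**The case against.** Four counter-arguments deserve weight.

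1. *The operative sections equate SCD with HbSS, and the analysis rows match that label.* This stands to the extent that the documents are inconsistent, rather than the SAP departing from one settled definition. It does not help the 20, who are then neither SCD, nor SCT, nor healthy for this test.
2. *The errors are not hidden.* Section 6.3 also asks for specificity, PPV and NPV, so trait calls would show in the HbAS row. A trait call for HbS/β⁰-thalassemia, which has no HbA, would also be an HbA false positive in the variant analysis, and exclusions must be reported. This stands. But Hypothesis 3 sets its threshold on sensitivity alone, and in the HbS variant analysis an SCD patient called trait is a true positive.
3. *β-thalassemia is Gazelle's task.* Gazelle does have the row, and Section 13 is candid about the sickling test. Neither gives these participants a class for Hypothesis 3.
4. *The size is illustrative.* This stands: *k* is assumed, and the equal weighting of HbSS and HbS/β-thalassemia comes from the recruitment quotas.

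A reader might infer three stronger claims that the documents do not support.
- That compound heterozygotes will be misread as trait. Section 13 points toward resemblance to HbSS; only the description of HbS/β⁺-thalassemia in 1.2 as mild points the other way. The direction is open.
- That the 40 HbS-free β-thalassemia participants go unused for this test. They are HbS negatives in the variant analysis, so HbS specificity rests on about 60 people, including these 40.
- That HbS/β-thalassemia is a common form of SCD locally. The 26% to 70% in 1.4 refers to hemoglobinopathies involving β-thalassemia of any kind, and no HbS/β-thalassemia frequency is given.

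**Conclusion.** The point holds as a gap in definition and scoring. The documents use two definitions of SCD, and under the named rows the 20 HbS/β-thalassemia participants have no reference class for the automated test. Whatever they are called, they cannot lower the SCD sensitivity; if called SCD, they count against HbSS specificity and PPV. This does not depend on guessing *k*.

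The numerical consequence does depend on it. Three or four misreads out of 20 would bring a combined SCD sensitivity down to 90.0%, while the HbSS row would still show 95% or 100%. This assumes that all 40 are scored and that Hypothesis 3 is judged on the point estimate. It is not evidence that the test will fail: if these samples look like HbSS, *k* would be near 0 and the combined figure would be as good as the HbSS one. The plan should be changed because, as written, its Hypothesis 3 sensitivity could not tell these outcomes apart.

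**What to change.** In 6.3, before the network is trained and scored:

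- Reconcile the SCD definition across 1.1, 1.3, 6.3 and 7.2.1, and state the reference class of each of the six HPLC phenotypes for the automated sickling test, including HbA/β- and Hbβ/β-thalassemia, which also have no row.
- Define *Overall*: which participants enter it, and what counts as agreement.
- Report SCD sensitivity for HbSS plus HbS/β-thalassemia against the 90% target, with HbSS-only and HbS/β-thalassemia-only sub-rows.
- Cross-tabulate the test's calls against all six HPLC phenotypes, so that misreads in either direction are visible.

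Keep the existing HbAA, HbAS and HbSS rows. There is no need to merge the training labels in 7.8 or to widen the healthy class to everyone without HbS; the latter would change the hypothesis.

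The cost is SAP wording and one extra table from data already being collected. The downside is that the reported SCD sensitivity may be lower than the HbSS-only figure.

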## 7.0 Detailed Research Procedures

# 7.1 Recruitment

The following procedure will be used for recruitment:

- 1) Potential participants may be patients diagnosed in Bheri Hospital or Mount Sagarmatha Polyclinic, or healthy volunteers.
- 2) Participants will have not given prior written permission to be contacted for research purposes. The participants will first be approached for the purpose of study recruitment by someone who is within their circle of clinical care. The health care professional will approach patients directly to advise them that a study is being conducted and to enquire if the patient would like to find out more information concerning it. With permission, patients may be referred to study staff.
- 3) The study coordinator or delegate will discuss in person (or virtually or over the telephone) potential study participation with candidates identified. The study Informed Consent Form (ICF) will be delivered to the interested patient for review during an inperson visit.
- 4) If after reviewing the ICF and/or discussing it with his/her family doctor and/or friends, the patient is interested in participating in the study, the study coordinator will arrange for an appointment to further discuss the study in detail. At that visit, the SC or delegate will meet with the patient to discuss the study and review all sections of the Informed Consent Form (ICF). An investigator will be available, if needed, to discuss any questions/ concerns the patient may have of a medical nature that the SC is not qualified to answer.
- 5) An investigator (e.g. [name]) will be available to discuss the medical aspects of the study, and to answer any questions related to the study. However, the investigator will not obtain consent or receive the participant's answer regarding their final decision, in order to mitigate the potential for undue influence over a prospective participant. The final consent will be obtained by the study coordinator, delegate or hospital staff.
- 6) If the patient remains interested in participating in the study, he or she will then sign the Informed Consent Form and the screening process will commence thereafter.

#### 7.1.1 Participants with HbS and/or β-thalassemia

All the participants with HbS and/or  $\beta$ -thalassemia (all participants excluding healthy volunteers) will be identified using the records of Bheri Hospital or Mount Sagarmatha Polyclinic in Nepalgunj. Records for the last 2-3 years will be accessed. Patients (and if applicable, their guardians) will be informed about the research trial and if willing to participate, informed consent will be obtained. The initial contact by delegate will happen either during in-person clinic visits or through telephone. Upon consent/assent, blood samples (3-4 mL) will be drawn for the research study (in addition to the routine bloodwork, if applicable).

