# 2.0 Study Purpose

The purpose of this study is to determine the accuracy of low-cost point-of-care techniques for screening and detecting sickle cell disease, sickle cell trait, and  $\beta$ -thalassemia, which will subsequently inform on feasible solutions for detecting the disease in rural, remote, or low-resource settings. One of the goals of the study is to evaluate the feasibility of techniques, such as the sickling test with low-cost microscopy and machine learning, HbS solubility test, commercial lateral-flow assays (HemoTypeSC and Sickle SCAN), and the Gazelle Hb variant test, to supplement or replace gold standard tests (HPLC or electrophoresis), which are expensive, require highly trained personnel, and are not easily accessible in remote/rural settings.

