# 5.0 Endpoints/Outcomes

The study has non-clinical endpoints (endpoints not relating to how a person feels, functions or survives, but which are objective indicators of biological processes) [44], with minimal intrinsic value to the participants of the current study, since most of the participants in the study will already know the diagnosis of SCD or SCT. However, the non-clinical endpoints are strongly associated with a meaningful clinical outcome of determining optimal screening alternatives for rural and remote communities.

**Primary endpoint/outcome**: Characterization of accuracy (sensitivity and specificity) of low-cost techniques, such as automated sickling test (standard sickling test enhanced using low-cost microscopy and machine learning), solubility test, HemoTypeSC, Sickle SCAN, and Gazelle Hb Variant test, for detecting sickle cell disease, sickle cell trait, and β-thalassemia, based on comparison with the gold standard test (HPLC).

**Secondary endpoint/outcome**: Training and testing of machine learning algorithm using deidentified images collected of blood films during sickling test. Assessment of whether a microscopy / machine learning based classification approach is suitable for deployment in rural areas in Nepal.

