# 6.0 Research Design

# 6.1 Research Plan and Design

The overall project has two phases:

- 1. Vancouver trials (September 2022 April 2023): With the help from hematologists and hematopathologists at BC Children's Hospital (BCCH) and St. Paul's Hospital (SPH), we plan to test the following screening techniques on patients with sickle cell disease (SCD) and sickle cell trait (SCT), and healthy participants:
  - a. Low-cost screening
    - i. Sickling test with low-cost automated microscope (such as Octopi microscope) and automated screening with machine learning
    - ii. HbS solubility test
    - iii. Commercial point-of-care assays (HemoTypeSC and Sickle SCAN)
    - iv. Gazelle Hb variant test
  - b. Gold standard test: HPLC, for determining the accuracies of low-cost screening techniques
- 2. **Nepal trials (October 2022 April 2023):** With help from [name], CP Nepal, UBC sickle cell team, and local lab technicians and health workers, we plan to screen the communities (e.g. in Nepalgunj) using the following:
  - a. Low-cost screening
    - i. Sickling test with low-cost automated microscope (such as Octopi microscope) and automated screening with machine learning
    - ii. Sickling test with traditional microscope (conventional manual screening used in Nepal)
    - iii. HbS solubility test
    - iv. Commercial point-of-care assays (HemoTypeSC and Sickle SCAN)
    - v. Gazelle Hb variant test
  - b. Gold standard test: HPLC, for determining the accuracies of low-cost screening techniques

This research protocol relates to the Nepal trials. There will be two ethics application submitted concurrently for the Nepal trials – one to the UBC Research Ethics Board and another to the Nepal Health Research Council.

To improve the transparency and completeness of reporting the findings (e.g. for publications resulting from this study), the checklist from the Standards for Reporting of Diagnostic Accuracy Studies or STARD 2015 will be followed [45]. The STARD 2015 guidelines was developed by experts to help reduce bias in diagnostic accuracy studies and to ensure that their reporting includes necessary information.

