#### 7.1.2 Healthy volunteers

For recruitment of normal participants or healthy volunteers, posters/flyers will be placed on bulletin boards at the study site (Mount Sagarmatha Polyclinic).

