### 7.2 Inclusion and Exclusion Criteria

#### 7.2.1 Inclusion Criteria

Since the techniques evaluated in the study aims at detecting sickle cell disease (SCD), sickle cell trait (SCT), and  $\beta$ -thalassemia, the following number of participants will be included in the study:

- 20 individuals with SCD (HbSS)
- 20 individuals with SCT (HbAS)
- 20 individuals with sickle cell/β-thalassemia compound heterozygous form (HbS/β-thalassemia)
- 20 individuals with β-thalassemia (Hbβ/β-thalassemia)
- 20 individuals with β-thalassemia trait or carrier form (HbA/β-thalassemia)
- 20 healthy individual participants or normal participants (HbAA, participants without any known hemoglobin disorders, such as SCD, SCT or β-thalassemia)

Participants older than 1 year of age at the time of drawing blood will be eligible. Signed and dated consent or assent forms will be required by the participants or their parents/guardians.

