# 12. Feasibility

Approximately 800 patients with SCA have been identified at Bheri Hospital and Mount Sagarmatha Polyclinic, and more with participants with sickle cell trait or  $\beta$ -thalassemia forms have been identified. Since the Bheri Hospital and Mount Sagarmatha Polyclinic are have HPLC machines, most patients from Nepalgunj and neighboring areas come to the hospital for diagnosis. Since Bheri hospital provides the diagnosis for free for SCD patients, the HPLC machine is relatively busy. The HPLC machine at Mount Sagarmatha Polyclinic is not as busy as that in Bheri hospital, which makes it more feasible to run the study at Mount Sagarmatha Polyclinic.

The hospital/clinic keeps a record of all patients, their diagnoses, and their contact information. As the number for each participant category is relatively small (i.e. 20 participants for each category), recruitment is feasible. We do not feel that additional participation in this study would be burdensome to patients and staff. We also plan to only recruit 20 healthy volunteers. We expect our recruitment efforts will assist in achieving this number.

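### Section 6.1 describes community screening, but section 7.1 recruits already-diagnosed patients and poster volunteers, so the results cannot by themselves establish community screening accuracy

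*Combined protocol and SAP*

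**What the plan says.** Two parts of the combined protocol and SAP describe the Nepal phase differently.

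- **Setting as announced.** Section 6.1 says "we plan to screen the communities (e.g. in Nepalgunj) using the following". Section 2.0 gives the purpose as "to determine the accuracy of low-cost point-of-care techniques for screening and detecting sickle cell disease", together with trait and β-thalassemia.
- **Recruitment as specified.** Section 7.1 says "Potential participants may be patients diagnosed in Bheri Hospital or Mount Sagarmatha Polyclinic, or healthy volunteers". Under 7.1.1 all participants with HbS or β-thalassemia "will be identified using the records of Bheri Hospital or Mount Sagarmatha Polyclinic in Nepalgunj", using the last 2-3 years. Under 7.1.2 the healthy group is recruited by posters and flyers at the polyclinic. Section 7.2.1 describes that group as "participants without any known hemoglobin disorders" and fixes 20 people in each of six phenotypes.
- **Status at entry.** Section 5.0 says that "most of the participants in the study will already know the diagnosis of SCD or SCT".
- **Conclusions aimed at.** The third current-study objective in 4.0 includes deciding whether the low-cost tests could replace HPLC or electrophoresis in rural and remote settings. The secondary endpoint in 5.0 includes whether the microscopy and machine-learning approach is suitable for deployment in rural Nepal.
- **Limitations.** Section 13 covers treatment, haplotype, and forms that some tests cannot separate or detect. It does not mention how participants are selected.

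**The concern.** Section 7 contains no community sampling. The plan first fixes who is affected from clinic records, recruits the unaffected by a separate route, and then measures the tests. A screening study would take people of unknown status and let the reference test sort them.

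The protocol itself gives reason to think the two populations differ. Section 1.4 says that detection programs are mostly urban while prevalence is higher in rural areas, and that limited rural screening leaves most affected people without access to the available support. People who have never been diagnosed cannot appear in the two facilities' records.

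At stake is what the results may be used for. A reader who relies on 6.1 would take the sensitivity and specificity as field screening results, and the third objective invites using them to decide on replacing HPLC in rural settings.

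**Working it through.** **1. The plan's own figure.** Six groups of 20 give 6 × 20 = 120, which matches the total in 6.3. The documents give no alpha, power, effect size or interval width, so nothing further can be reproduced.

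**2. The sections side by side.**

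| Feature | 6.1 as worded | 7.1, 7.2.1 and 5.0 as specified |
|---|---|---|
| Source of affected people | Communities | Records of two facilities, last 2-3 years |
| Source of unaffected people | Communities | Responders to posters at the polyclinic |
| Status before testing | Unknown, if this is screening | Mostly known |
| Mix of phenotypes | Whatever the community yields | About 20 in each of six groups |

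The Vancouver entry in 6.1 speaks of testing the techniques on patients with SCD and SCT and on healthy participants. That wording would fit the Nepal recruitment better than the wording used for Nepal.

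**3. Who the negatives are.** Under the variant analysis in 6.3, a person lacking HbS counts as HbS-negative whatever other variants are present.

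- HbS-positive: HbSS 20 + HbAS 20 + HbS/β-thalassemia 20 = 60.
- HbS-negative: HbAA 20 + HbA/β-thalassemia 20 + Hbβ/β-thalassemia 20 = 60, of whom 40 (two thirds) have a β-thalassemia genotype.

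For HbS, then, the comparison is not simply patients against healthy controls.

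**4. Could selection within a phenotype matter?** The documents suggest that it could for some tests. Manual sickling in 7.5.1 uses a graded cut-off (more than 25% of cells sickled or deformed). Section 1.6 links sickled-cell shape to HbS concentration and rate of deoxygenation. Section 1.5 links false-negative solubility results to low HbS. Section 13 says treatment may affect how the sickling test reads.

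The direction is not fixed. Clinic patients may be treated while undiagnosed people are not, and that difference could push the clinic estimate down as well as up. The documents give neither the share of community cases that differ from recorded ones nor the accuracy in them, so no bias can be calculated.

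**5. Could this study have sampled the community instead?** Section 1.7 gives prevalences of about 10% (SCD and SCT, Tharu community in Dang) and about 25% (Nepalgunj).

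- For 60 HbS-positive people: 60/0.10 = 600, or 60/0.25 = 240.
- For 20 HbSS people, assuming Hardy-Weinberg proportions (not in the documents), the allele frequency is q = 1 − √(1 − p). At p = 0.10, q = 0.0513, q² = 0.00263 and 20/q² ≈ 7,595. At p = 0.25, q = 0.1340, q² = 0.01795 and 20/q² ≈ 1,115.

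Against the 1-3 months in 6.2, recruiting known cases is an understandable choice. The fault lies in how it is described and in what is concluded from it.

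**6. Choice of patients within the records.** Section 7.1 gives no order of approach. Its step 6 starts screening only after consent is signed, so no log is promised of people approached who decline.

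**The case against.** The strongest reply is that this is one loose phrase. Sections 5.0, 6.3, 7.1, 7.2.1, 8.0 and 12 consistently describe a clinic study with fixed groups. Section 5.0 openly says that most participants know their diagnosis, and 7.8 says the algorithm will not be used to diagnose new patients. Community implementation is a long-term objective in 4.0, and the third objective asks only about potential replacement. Section 12 adds that most patients from Nepalgunj and neighbouring areas come to be diagnosed where HPLC is available.

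Much of this stands. The design is a defensible early step and gives useful accuracy estimates by phenotype. But the rural replacement question and the rural deployment question are set for the current study, and section 13 does not qualify either.

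Two stronger readings are tempting and are not supported:

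- **That the sample consists of easy cases, so that accuracy will be inflated.** No section selects on severity or on a clear HPLC pattern. Two of the six groups (40 of 120) are trait carriers, and section 1.1 says sickle cell trait usually shows no hematological abnormality. Section 1.2 calls HbS/β⁰-thalassemia hard to tell from HbSS, and section 13 expects treated patients. The healthy group needs only to have no known disorder. If community prevalence applied to it, 20 × 0.10 = 2 to 20 × 0.25 = 5 volunteers would carry HbS undiagnosed.
- **That 20 HbSS participants out of the total in section 12 gives the sampling fraction.** That section says "Approximately 800 patients with SCA have been identified at Bheri Hospital and Mount Sagarmatha Polyclinic" without giving a period. Recruitment uses 2-3 years of records and excludes recent transfusion and pregnancy, so the eligible number is unknown.

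**Conclusion.** The inconsistency between 6.1 and 7.1 is real, and the plan is wrong as written on this point. The study that will be run measures accuracy in previously diagnosed patients of two facilities and in poster volunteers. It can support estimates by phenotype in those people. It cannot by itself establish accuracy in undiagnosed people in rural communities.

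The size and direction of any difference are unknown, and a numerical illustration would rest wholly on assumed inputs. The conclusion rests only on the recruitment text and on section 1.4's account of rural access; it does not assume that recorded patients are easier to classify.

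This does not invalidate the study. It limits what the third objective and the secondary endpoint may conclude, and it should be corrected before results are read as screening performance. Predictive values computed at the fixed mix (60/120 = 50% HbS-positive) are a separate matter.

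**What to change.** 1. **Section 6.1.** Describe the Nepal phase as a clinic-based accuracy study in previously diagnosed patients and healthy volunteers, in place of the community-screening wording.
2. **Third objective (4.0), secondary endpoint (5.0) and section 13.** Limit conclusions to that population. Add the selection of participants as a limitation, and state that community screening accuracy must be shown in a separate unselected sample before any claim that HPLC can be replaced.
3. **Section 7.1.1.** List the eligible recorded patients in each phenotype, approach them in random order, and log refusals and ineligibles. This also helps meet the commitment in 6.1 to report by STARD 2015. It removes discretion over who is approached within the records but does not close the gap between clinic and community, so items 1 and 2 are still needed.

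The cost is protocol wording, a randomised call list, some extra contacts and a more modest conclusion. No additional participants are required.
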